Official Study Title

Biomarker Studies to Predict Treatment Outcomes of Enfortumab Vedotin in Advanced Urothelial Carcinoma

ClinicalTrials.gov Identifier (NCT Number): Pending Assignment

Document Date: June 19, 2025

Confidentiality Notice:

This document is intended for use in the ClinicalTrials.gov registration and results reporting process only. It does not contain any personal identifiers of study participants.

1. Official Study Title

Biomarker Studies to Predict Treatment Outcomes of Enfortumab Vedotin in Advanced Urothelial Carcinoma

2. Background and Rationale

Advanced urothelial carcinoma (aUC) remains a highly fatal malignancy, with limited durable responses to first-line platinum-based chemotherapy. Enfortumab vedotin (EV), a nectin-4-targeting antibody-drug conjugate, has shown promising efficacy in aUC patients, both in the first-line setting when combined with pembrolizumab and in later-line setting when used as monotherapy (EV/EVP). However, despite its clinical success, the occurrence of significant toxicities and high treatment costs highlight the need for predictive biomarkers to optimize treatment outcomes and mitigate adverse effects. Nectin-4, as the target of EV, along with ADAM10/17, enzymes responsible for nectin-4 shedding, and soluble nectin-4 (sNectin-4), have emerged as potential biomarkers for predicting EV treatment outcomes.

3. Objectives

3-1. Primary Objective

(1) To investigate the correlation between membranous nectin-4 (mNectin-4) expression and treatment outcomes in patients with aUC receiving EV/EV-P.

3-2. Secondary Objectives

(1) To evaluate the association between ADAM10/17 expression and treatment outcomes of EV/EVP in aUC.

(2) To examine the relationship between sNectin-4 levels and treatment efficacy of EV/EVP in aUC patients.

3-3. Exploratory Objective

(1) To assess whether mNectin-4, ADAM10/17, and sNectin-4 can serve as predictive biomarkers for EV/EVP in aUC patients.

4. Study Design

4-1. Study Type: Observational

4-2. Study Design: Prospective cohort study

4-3. Study Center: Single-center (National Taiwan University Hospital, NTUH); may expand to

multi-center in the future

4-4. Enrollment Method: Consecutive enrollment of eligible patients

4-5. Study Period: April 1, 2025 to December 31, 2029

4-6. Estimated Sample Size: 100 patients receiving EV/EVP, plus 100 patients treated with platinum-

based chemotherapy as a comparator cohort

5. Study Population

5-1. Inclusion Criteria

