(1) Histologically confirmed diagnosis of advanced aUC, including bladder cancer or upper tract urothelial carcinoma

(2) Age \geq 20 years

(3) Received EV/EVP or first-line platinum-based chemotherapy at NTUH

- (4) Availability of archival formalin-fixed paraffin-embedded (FFPE) tumor tissue for biomarker analysis
- (5) Willingness to provide serum samples at predefined time points
- (6) Ability to provide written informed consent

5-2. Exclusion Criteria

- (1) Patients who have received prior investigational agents targeting nectin-4
- (2) Inadequate tissue samples or insufficient serum collection
- (3) Concurrent participation in another interventional clinical trial
- (4) Any condition that, in the investigator's judgment, would compromise the patient's safety or compliance with study procedures

5-3. Sampling Method

- (1) Consecutive enrollment of eligible patients meeting the inclusion criteria

5-4. Estimated Sample Size

- (1) 100 patients treated with EV/EVP
- (2) 100 patients treated with first-line platinum-based chemotherapy (for comparative biomarker analysis)

6. Study Groups/Cohorts

6-1. Group 1: EV Therapy Cohort

- (1) Population: Patients with aUC receiving EV/EVP at NTUH
- (2) Treatment: Standard EV-based regimen (monotherapy or in combination with pembrolizumab)
- (3) Biospecimen Collection:
 - Archival tumor tissue for immunohistochemistry (IHC) analysis of mNectin-4 and ADAM10/17 expression
 - Serum samples collected at predefined time points for sNectin-4 quantification via ELISA

(4) Clinical Data Collection: Demographics, disease characteristics, treatment details, response assessments (RECIST), progression-free survival, overall survival, and adverse events

6-2. Group 2: Chemotherapy Cohort (Comparator Cohort)

(1) Population: Patients with aUC who received first-line platinum-based chemotherapy at NTUH during the same enrollment period

(2) Treatment: Standard first-line cisplatin- or carboplatin-based chemotherapy

(3) Biospecimen Collection:

- Archival tumor tissue for IHC analysis of mNectin-4 and ADAM10/17
- Serum samples for sNectin-4 quantification

(4) Clinical Data Collection: As per EV therapy cohort, for comparative analysis

7. Endpoints / Outcome Measures

7-1. Primary Outcome Measure

(1) Objective Response Rate (ORR): Proportion of patients achieving complete or partial tumor response according to RECIST 1.1 criteria after enfortumab vedotin treatment. Time Frame: Up to 12 months after treatment initiation

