7-2. Secondary Outcome Measure

(1) Progression-Free Survival (PFS): Time from treatment start to disease progression or death from any cause. Time Frame: Up to 24 months

(2) Overall Survival (OS): Time from treatment initiation to death from any cause. Time Frame: Up to 36 months

(3) Treatment-Related Adverse Events: Incidence and severity of adverse events graded by CTCAE v5.0

during treatment. Time Frame: Throughout treatment duration

(4) Correlation of Biomarker Expression with Treatment Outcomes: Association between mNectin-4, ADAM10/17 expression, serum sNectin-4 levels, and clinical outcomes. Time Frame: Assessed at baseline and during follow-up

8. Methods / Assessments

8-1. Sample Collection

(1) Tumor Tissue:

- Archival formalin-fixed paraffin-embedded (FFPE) tumor specimens will be retrieved from diagnostic pathology samples.
- Tumor samples will be analyzed for mNectin-4 and ADAM10/17 expression by IHC.

(2) Serum Samples:

- Blood samples will be collected at predefined time points: before the initiation of systemic therapies/at first radiographic response assessment (approximately week 6–8)/t disease progression or end of treatment
- Serum will be isolated and stored at –80°C for subsequent analysis of sNectin-4 by ELISA.

8-2. Biomarker Analysis

(1) IHC:

- FFPE tissue sections will be stained for nectin-4 and ADAM10/17 using validated antibodies.
- Expression will be semi-quantitatively scored based on H-score and/or staining intensity and proportion.

(2) Enzyme-Linked Immunosorbent Assay (ELISA):

- Serum sNectin-4 levels will be quantified using a commercially available ELISA kit following manufacturer's instructions.

8-3. Statistical Analysis

- (1) Descriptive statistics will be used to summarize patient characteristics and biomarker distributions.
- (2) Group comparisons:
 - Mann-Whitney U test or t-test for continuous variables
 - Chi-square or Fisher's exact test for categorical variables
- (3) Survival analysis:
 - Kaplan-Meier method for estimating PFS and OS
 - Log-rank test for between-group comparisons
- (4) Multivariable analysis:
 - Cox proportional hazards model to assess the independent association of biomarkers with survival outcomes
 - Logistic regression for associations with objective response

9. Ethics / Regulatory Compliance

9-1. The study protocol has been reviewed and approved by the Research Ethics Committee E of National Taiwan University Hospital.

IRB Approval Number: 202502065RINE

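### The adverse event outcome in 7-2(3) ends with treatment, so treatment-related events, worsening and fatal outcomes after that point fall outside it

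*Protocol*

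**What the plan says.** Protocol section 7-2(3) defines the third secondary outcome as "Treatment-Related Adverse Events: Incidence and severity of adverse events graded by CTCAE v5.0", and then limits it twice in succession: "during treatment. Time Frame: Throughout treatment duration". Neither the end of treatment nor any period after the last dose is defined.

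The two time-to-event outcomes in the same section are not tied to treatment. PFS is "Time from treatment start to disease progression or death from any cause. Time Frame: Up to 24 months" and OS is "Time from treatment initiation to death from any cause. Time Frame: Up to 36 months".

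Section 6-1(4) lists the data collected in the EV cohort, ending with "progression-free survival, overall survival, and adverse events", and sets no start or end for adverse events. Section 6-2(4) applies the same list to the platinum cohort: "Clinical Data Collection: As per EV therapy cohort, for comparative analysis".

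The Background (section 2) gives toxicity, beside cost, as a reason for the study: "the occurrence of significant toxicities and high treatment costs highlight the need for predictive biomarkers to optimize treatment outcomes and mitigate adverse effects".

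**The concern.** The end of the window is not independent of what is being measured. Toxicity is one of the reasons treatment stops, and when it does, the window closes on that patient while the event may still be evolving. The patients with the worst toxicity can therefore have the shortest window.

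Three things then fall outside the outcome: a treatment-related event that begins after treatment has ended, a rise in grade of an event that led to stopping, and a fatal outcome that follows stopping. The second and third bear directly on severity, which 7-2(3) sets out to measure.

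The platinum cohort supplies the same data for comparison, and the regimens differ (EV alone, EV with pembrolizumab, cisplatin- or carboplatin-based). Nothing in the protocol ensures that the uncounted share is the same in each. A toxicity rate reported by cohort or by marker level would carry that uncertainty.

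**Working it through.** **No figure to reproduce.** The protocol gives no adverse event rate, power or effect size for this outcome. The check is a reading of every statement on adverse events and follow-up, followed by an illustration on assumed rates.

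**Step 1: which sections could extend the window?**

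- 7-2(3) states the window as the treatment period, twice.
- 6-1(4) and 6-2(4) name adverse events as data, with no window.
- 7-2(4) mentions follow-up for the biomarker associations, but does not change the adverse event outcome that would feed them.
- 8-3 adds no safety period.
- No section follows open events to their peak grade or attributes deaths to treatment.

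**Step 2: follow three patients through the outcomes as written.**

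| Patient | 7-2(3) | PFS and OS |
|---|---|---|
| Stops for a grade 3 toxicity that later resolves | counted, grade 3 | not affected by the toxicity |
| Stops for a grade 3 toxicity that rises to grade 4 after treatment | counted, grade 3 | not affected by the toxicity |
| Stops for a grade 3 toxicity and dies of it after treatment | counted, grade 3, not grade 5 | death is an OS event within 36 months, and a PFS event within 24 months if there was no earlier progression |

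A fourth patient, whose first treatment-related event begins after treatment ends, is not counted in 7-2(3) at all.

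**Step 3: how large could it be? (assumed rates, none from the documents)**

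Let p be the true share of patients with an event of a given severity, and f the share of those who first reach that severity after treatment ends. The outcome as written shows p × (1 − f). In 100 patients (the planned size of each cohort, section 4-6), 100 × p × f are not counted.

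| p | f = 5% | f = 10% | f = 20% | f = 30% |
|---|---|---|---|---|
| 20% | 19% | 18% | 16% | 14% |
| 40% | 38% | 36% | 32% | 28% |
| 60% | 57% | 54% | 48% | 42% |

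For p = 40%, that is 100 × 0.40 × 0.05 = 2 patients up to 100 × 0.40 × 0.30 = 12 patients per 100.

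**Step 4: what if f differs between cohorts?** Let both have p = 40%. The probability that a two-sided 5% comparison of two proportions, with 100 patients per cohort, declares a difference produced only by the window is:

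- f = 5% against 20%: 38% against 32% observed, probability about 14%.
- f = 10% against 30%: 36% against 28% observed, probability about 23%.
- f = 5% against 30%: 38% against 28% observed, probability about 32%.

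**Step 5: fatal events.** Assume a 2% treatment-related death rate. The probability that at least one appears as grade 5 among 100 patients is 1 − (1 − 0.02 × (1 − f))^100. This gives 87% when none occurs after treatment (f = 0), 63% when half do, and 0% when all do.

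**The case against.** The strongest reply has four parts.

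**Outcome window, not collection rule.** A reader might infer that recording of adverse events stops with treatment, so that later events and toxic deaths are lost to the study. The documents do not support this. Section 7-2(3) sets the time frame of an outcome. Sections 6-1(4) and 6-2(4) govern collection and give no end date, so later events may well be recorded. The toxicity that stops treatment is itself counted, at the grade reached by then, and later deaths remain in PFS and OS. This part stands and fixes the scope of the point.

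**Undefined end.** The protocol does not define the treatment period, and a SAP that is not shown could include some days after the last dose. The document is also written for registration, where time frames are short. This stands only in part. The limit is stated, not left open, and a SAP that followed the wording would inherit it.

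**Little rests on it.** No objective in section 3 names toxicity, the models in 8-3(4) cover survival and response only, and the study is observational. Toxicity enters through one Background sentence and, at most, through the clinical outcomes of 7-2(4). This stands as a limit on importance. It does not make the secondary outcome itself sound.

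**Bias not shown.** Nothing in the documents shows that late events differ by regimen or marker level. If the uncounted share is similar across groups, absolute rates fall without necessarily creating a false association. This also stands: unequal loss is a possibility, not a result.

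**Conclusion.** The point holds as a limit in the stated outcome definition. Applied as written, 7-2(3) leaves out treatment-related events that begin after treatment ends, later worsening of events that led to stopping, and later fatal outcomes. The direction is known: incidence and severity can only be understated, and the window closes early for patients who stop because of toxicity.

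The size is not known. It depends on p and f, for which the protocol gives no values; across the assumed ranges above, 1 to 18 patients per 100 would be missed. The figures for unequal loss need the further assumption that f differs between cohorts. A reader might conclude from them that the cohort comparison is biased, but the documents do not establish that.

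This is a descriptive secondary outcome, and neither the primary outcome nor the survival analyses are affected. The change is worth making because it is cheap and because toxicity is part of the stated rationale.

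**What to change.** Replace the time frame in 7-2(3) with one on these lines: from first dose until a fixed number of days after the last dose or the start of the next systemic therapy, whichever comes first. The sponsor sets the number of days, and it is the same in both cohorts.

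Add three rules:

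- Events still open when the window closes are followed to maximum grade and outcome, including death.
- Deaths within the window are recorded with attribution to treatment.
- A treatment-related death reported after the window, other than as the outcome of an event already being followed, is listed separately. All grades in the main table then share one window for onset. Counting grade 5 over the whole of OS follow-up would give it a different window from the other grades.

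The cost is a few sentences in 7-2(3), a matching field on the case report form, and some extra chart abstraction. Patients are already followed for PFS and OS, but that does not by itself ensure that CTCAE grades are recorded after treatment, so the abstraction has to be planned. Reported toxicity will look slightly less favourable. The protocol is dated June 19, 2025 and the planned start was April 1, 2025, so the change is best made while few patients would need retrospective review.

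### Could the sNectin-4 sample drawn at progression produce a false association with PFS or OS?

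*Protocol*

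**What the plan says.** Section 7-2(4) defines one pooled secondary outcome: "Association between mNectin-4, ADAM10/17 expression, serum sNectin-4 levels, and clinical outcomes". Its timing is given only as "Time Frame: Assessed at baseline and during follow-up".

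The two tissue markers come from archival specimens, so sNectin-4 is the only marker with repeated values. Section 8-1(2) sets its draws before systemic therapy, at the first response scan at about week 6–8, and at "disease progression or end of treatment".

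PFS is defined in section 7-2(1) as "Time from treatment start to disease progression or death from any cause", followed for up to 24 months. OS in section 7-2(2) has the same starting point and is followed for up to 36 months. Section 8-3 lists descriptive summaries, Kaplan-Meier curves, log-rank tests, logistic regression for response, and a "Cox proportional hazards model to assess the independent association of biomarkers with survival outcomes". It does not say which draw enters any of them.

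The objectives concerned are secondary objective 3-2(2), "To examine the relationship between sNectin-4 levels and treatment efficacy of EV/EVP in aUC patients", and exploratory objective 3-3(1), which asks whether the markers "can serve as predictive biomarkers for EV/EVP in aUC patients".

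**The concern.** For a patient treated until progression, the third draw is taken at the PFS event itself. If sNectin-4 rises or falls steadily on treatment, patients who progress later have had more time to drift before that sample. The value then encodes time to progression even when the marker has no bearing on outcome. Entered as a fixed covariate in a Cox model from treatment start, it would show an association created by the timing of the draw. OS would be affected too, because time to progression is part of OS.

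The time frame names baseline and follow-up together, and nothing in the text excludes this use of the third draw. If it happened, the answer to objective 3-2(2), and any claim about prediction under 3-3(1), could be an artefact. A value obtained at progression cannot predict that progression.

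**Working it through.** The protocol states no figure on this point, so there is none to reproduce. The check has two parts: whether the mechanism is real, and whether the protocol plans the analysis that triggers it.

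**1. The mechanism.**

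Inputs from the protocol: 100 EV/EVP patients; PFS cut off at 24 months and OS at 36 months; both counted from treatment start.

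Assumed inputs, not in the protocol: exponential PFS with median 6 or 12 months; independent post-progression survival with median 6 months; baseline log sNectin-4 distributed N(0,1) and unrelated to any outcome; measurement noise 0.3 SD; 20% of patients ending treatment before progression; linear drift as shown in the table.

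Model for the last draw: value = baseline + drift × months to the draw + noise. Only patients with that draw by month 24 were analysed. Each setting used 2,000 cohorts and a two-sided 5% Cox score test. The Monte Carlo standard error at 5% is √(0.05 × 0.95 / 2000) = 0.5 points.

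False-positive rates for the last draw (median PFS 6 / 12 months):

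| Drift, SD per month | PFS from treatment start | OS from treatment start | OS counted from a progression draw |
|---|---|---|---|
| 0 | 5.4% / 5.8% | 5.0% / 5.0% | 5.0% / 5.4% |
| 0.02 | 14.8% / 12.0% | 8.0% / 7.3% | 6.0% / 4.6% |
| 0.05 | 57.6% / 50.0% | 23.2% / 25.8% | 5.6% / 6.1% |
| 0.10 | 98.3% / 93.2% | 60.0% / 63.6% | 6.0% / 5.1% |
| −0.05 | 60.8% / 49.6% | 24.4% / 25.4% | 5.2% / 5.8% |

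The median false hazard ratio for PFS is 0.81 per baseline SD at drift 0.05 and reverses to 1.24 at −0.05.

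Other draws on the same data:
- Pre-treatment draw: 4.7–6.0% for PFS and 4.7–5.8% for OS.
- Week 6–8 draw with a landmark at 1.6 months: 4.9–6.2% for PFS and 4.3–5.6% for OS.

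A second simulation used a between-patient SD of 0.5 on the log scale, responder and non-responder PFS mixtures, and 0–40% early stopping. It gave 5–7% for PFS with no drift, 24–42% at 0.02 log units per month and 80–98% at 0.05. In SD units those drifts are 0.02 / 0.5 = 0.04 and 0.05 / 0.5 = 0.10, so the two sets of results are compatible.

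The mechanism is therefore real, and its size depends on the drift. A drift of 0.05 log units per month means a rise of exp(0.05 × 12) = 1.8-fold over 12 months and exp(0.05 × 24) = 3.3-fold over 24 months. The protocol neither states nor implies any such figure.

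**2. What the protocol plans.**

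- Section 7-2(4) covers three markers and the outcomes in one timing line. Markers at baseline with outcomes in follow-up is one fair reading. Markers measured at several times is another. Neither says that every measured value enters a model from treatment start.
- Section 8-3 asks for a Cox model. A baseline covariate, a landmark analysis and a time-dependent covariate are all Cox models.
- Section 8-3(1) provides for descriptive summaries of biomarker distributions, a natural place for the last draw.
- The study title and objective 3-3(1) speak of prediction, which points to the pre-treatment draw.

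No passage plans the harmful analysis.

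**The case for a change.** The strongest argument for a change is that ORR, PFS and OS already have their own time frames of 12, 24 and 36 months, and none of them can be assessed at baseline. On that view the line in section 7-2(4) reads more naturally as marker timing. It then pools a pre-treatment value with one triggered by the event, within a named secondary outcome of a document written for registration. A few sentences would settle it, need no new samples, and prevent choosing the draw after seeing which one associates.

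Part of this stands. The text is open, and the draw for each outcome should be fixed before the data are examined. But marker timing says when samples are measured, not how they are modelled. Which serial sample enters which model, and whether by landmark or as a time-dependent covariate, is commonly left to the SAP, which is not at hand. The absence of a prohibition is not a plan to do the wrong analysis. An analyst who intends prediction would not ordinarily enter a sample drawn at progression as a predictor of PFS.

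**Conclusion.** The concern does not require a change to the protocol. The ambiguity is real but it is a gap that the SAP would ordinarily fill, and sound analyses of all three draws fit the methods already listed. Pre-treatment sNectin-4 can serve as the predictor from treatment start, the week 6–8 value can be handled by landmark or as a time-dependent covariate, and the last draw can stay descriptive or be related only to survival after it. In the simulations of these inferential uses, error rates stayed at about 4–6%.

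The large false-positive rates need two things the protocol does not supply: use of the last draw as a fixed covariate from treatment start, and a systematic drift whose size is assumed. Without drift the rate stays near 5%. The reach is also small: one marker, in one secondary and one exploratory objective of an observational study. The primary objective (mNectin-4) and primary outcome (ORR) are untouched. If the SAP is silent on the draw, it is the place to state it.
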